### Control Group

The patient will receive 10 U of regular insulin + Dextrose 50% over 30 minutes + salbutamol nebulization 10mg in 3ml normal saline over 15min, calcium gluconate will be given according to the physician responsible about the case.

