## **7. Study flow**

The study protocol will be for a total of 2 hours. All groups will follow the same path except the dose of insulin administered. After the result of potassium level ( $\geq 5.5$  mEq/L) patient will be screened for inclusion and exclusion criteria at the same time all other medications except insulin can be administered as the doses are fixed. Eligible patient will have to sign a

written consent if they agreed to be involved in our study. The initial data and basic labs will be collected before starting the study protocol. The incharge doctor/investigator will take the random code and write it on the data collection sheet of that patient from already prepared list/code and give the assigned nurse the medications administration card/form (see appendix: [medications administration form](#)).

Every patient will receive:

- Potassium lowering agent:
    - Intravenous Regular insulin 5 units **OR** 10 units with Glucose 50% water 50 ml over 30 minutes according to the randomization.
    - Salbutamol nebulization 10 mg in 3ml normal saline over 15 minutes.
  - The physician will decide the need of cardiac stabilizing agents (e.g Calcium Gluconate) as indicated by the physician in-charge of the patient.
- Please see [study flow chart](#) in the attachment.

5 Units insulin group	10 units insulin group
Medications to be administered: • IV Insulin Regular 5 units with Dextrose 50 % 50 ml over 30 minutes. • Salbutamol 10 mg NEB over 15 minutes.	Medications to be administered: • IV Insulin Regular 10 units with Dextrose 50 % 50 ml over 30 minutes. • Salbutamol 10 mg NEB over 15 minutes.

Figure 1: Treatment. RBS: Random Blood sugar. IV: Intravenous. NEB: Nebulization.

Initial investigations will include:

ECG, Urea and electrolytes, Creatinine, eGFR, Random blood sugar, complete blood count, Magnesium level, bone profile, phosphate level, will be attached if not sent before.

Repeated labs will be with these frequencies:

**Potassium** level: 0 and 120 minutes from medications administration time.

**Blood sugar**: 0, 60 and 120 minutes from medications administration time.

The study will be over at 2 hours (120 minutes) or by patient decision to withdraw from the study.

	0	Post involvement	
		60	120
Timeline (minutes) from medications administration	0	60	120
Eligibility screen	*		
Consent	*		
Randomization	*		
Basic labs: ECG, U&E, RBS, CBC, Mg, bone profile, PO4, VBG.	*		
Study Medication administration	* →		

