## Salbutamol

### Method for Application of Salbutamol Nebulization

1. Preform hand hygiene and don clean gloves.
2. Take 10 mg of insulin.
3. Mix it with 3 ml of Sodium Chloride 0.9%.
4. Put it on Nebulization devise.
5. Run it for 15 minutes
6. Disconnect and discard all materials in their proper disposal bins.
7. Remove gloves and preform hand hygiene.

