## 22. Quality control and quality assurance.

### Preparation quality

- A study approval from the Royal Hospital and Sultan Qaboos University hospital review board obtained.
- Ensure that all required documents (data collection sheet, informed consent), randomization packages are in order and easily accessible for the investigators.
  - o **Investigator's brochure**
- To document that relevant and current scientific information about the investigational product has been provided to the investigator.
  - o **Signed protocol.**
  - o **Informed consent form.**
  - o **Subject Deviation/Unanticipated Problem Case Log.**
  - o **Serious Adverse Event (SAE) Case Log.**
  - o **Withdrawal log.**

- **Nurses and physicians who are involved in the data collection will be trained in the following areas:**
  - o Full description of the attended study and the way to obtain research consent.
  - o Obtaining potassium level from official biochemistry lab result
  - o Preparing Intravenous insulin/Dexstrose 50% + Salbutamol Nebulization.
  - o Measurement of possible side effected and secondary outcomes.

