## 27.Appendix:

### Data collection sheet

Patient hospital ID								
Study Code:								
Demographics								
Hospital								
Location (ED/Inpation)								
Gender								
Age								
DM type								
HTN								
IHD								
ESRD								
Last Dialysis session (if any)								
Other comorbidities								
Home Medications								
Suspected cause of Hyperkalemia								
CBC	Hb:	WBC:	Plat:					
UE	AG:	HCO3:	Creat:	GFR:	Na:	K:		
Mg serum								
Follow up /time line (minutes)	0	60	120					
Potassium								
Blood sugar								
Total amount of Intravenous fluid received during the study period / type of IV fluid								
Other medications administered								
Urine output (if any)								
Needed another antihyperkalemic messures?								
Needed Urgent/Emergent Dialysis?								

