## Medications administration form:

### Medications administration card

(Insulin 5 units group)

- The doctor **must not know** the dose of insulin received by the patient.
- Give the patient the following medications:
  - Insulin Regular 5 units with Dextrose 50 ml of 50 % concentration intravenously (IV) over 30 minutes.
  - Salbutamol 10 mg Nebulization over 15 minutes.

Please repeat potassium level after 120 minutes from the time insulin/dextrose infusion

Repeat RBS: 60 and 120 minutes.

	60 minutes	120 minutes
Serum Potassium measurement		*
*RBS via glucometer	*	*

- If a patient become hypoglycemic (random blood sugar (RBS)  $\leq$  3.89 mmol/l in Diabetic patients and less than 3 mmol/l in non-Diabetic patients) inform the Doctor/Research assistant.
- Example: if you start insulin/Dextrose at 02:00 the infusion till 02:30 so repeat RBS at 03:00 and 04:00. Repeat U&E at 04:00.
- \*RBS: Random blood sugar. U&E: urea and electrolytes.

---

---

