## Attending physician

1. Patient will receive Salbutamol nebulization 10 mg in 3ml normal saline over 15 minutes.
2. ((The physician will decide the need of cardiac stabilizing agents (e.g Calcium Gluconate) as indicated by the physician in-charge of the patient.))
3. Will screen inclusion and exclusion criteria.
4. Explain all study procedure to the patient.
5. Obtain informed consent with signature.

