## Randomization

1. Open study envelope.
2. Take the included code in that envelope and stick it to the patient data collection sheet.
3. Give medication instructions card to the nurse in-charge of the patient

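### The salbutamol preparation step names insulin, and nothing tells the nurse to omit salbutamol already given before randomisation

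*Protocol*

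**What the plan says.** **Preparation.** In Protocol section 8, under the heading for the salbutamol nebulization method, step 2 reads "Take 10 mg of insulin". The next steps mix the drug with 3 ml of saline, load a nebulizer and run it for 15 minutes.

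**Regimen.** Section 5 gives the control arm "salbutamol nebulization 10mg in 3ml normal saline over 15min" and uses the same words for the intervention arm. Section 7 also lists one 10 mg nebulization for every patient.

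**Timing.** Section 7 says that during screening "all other medications except insulin can be administered as the doses are fixed". In the study flow chart (Appendix), step 1 of the attending physician's box is "Patient will receive Salbutamol nebulization 10 mg in 3ml normal saline over 15 minutes". Screening, explanation and consent come after it in the same box. The randomisation box follows and ends with "Give medication instructions card to the nurse in-charge of the patient".

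**The card.** The medications administration card (Appendix) tells the nurse to give the listed drugs, including "Salbutamol 10 mg Nebulization over 15 minutes". It does not mention salbutamol already given.

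**Records and training.** The data collection sheet has no salbutamol field, only the general line "Other medications administered". Section 22 lists "Preparing Intravenous insulin/Dexstrose 50% + Salbutamol Nebulization" among the training topics.

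**The concern.** These are working instructions for staff who prepare and give drugs in an emergency department. Two things are wrong with them.

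First, a preparation step names the wrong drug. Insulin is the drug under test and is handled in the same treatment episode, so it is the name most easily confused here.

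Second, the same salbutamol dose appears at two successive steps, first for the physician and then for the nurse, with nothing linking them. A nurse who does exactly what the card says could repeat a nebulization already given. That would be an unplanned extra dose of a potassium-lowering drug. Section 24 counts incorrect drug administration as a protocol violation, so a violation could arise from following the card correctly. With no salbutamol field on the data sheet, a repeat might also be hard to see afterwards.

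**Working it through.** This is mainly a comparison of texts. The only arithmetic is the total dose.

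**1. Which drug does step 2 mean?**

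| Place in the Protocol | Drug and dose |
|---|---|
| Section 5, Control Group | salbutamol 10 mg |
| Section 5, Intervention Group | salbutamol 10 mg |
| Section 7, Study flow (list and treatment table) | salbutamol 10 mg |
| Appendix, medications administration card | salbutamol 10 mg |
| Appendix, flow chart, attending physician | salbutamol 10 mg |
| Section 8, salbutamol method, step 2 | insulin 10 mg |

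The heading, the unit (mg) and the route (nebulizer) all point to salbutamol. The two insulin methods in section 8 dose insulin in units and give it through a venous cannula. No reading makes step 2 correct, so it is an error of drug name.

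**2. How much salbutamol do the instructions lead to?**

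Intended dose, from sections 5 and 7: 10 mg, once.

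The flow chart and then the card allow three paths:

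- Not given during screening, card followed: 0 + 10 = 10 mg.
- Given during screening, nurse omits it from the card: 10 + 0 = 10 mg.
- Given during screening, card followed as printed: 10 + 10 = 20 mg, and 20 / 10 = 2 times the intended dose.

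The second path needs the nurse to depart from the card, which does not invite this. The third path is what results when the flow chart and the card are each carried out as written.

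**3. Are the arms affected differently?**

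Sections 5 and 7 give the same salbutamol regimen to both arms, and the early dose comes before randomisation. Both printed copies of the card are headed as the 5-unit group; no 10-unit card is shown. That the 10-unit card carries the same unconditional line is therefore inferred from sections 5 and 7, not read from the card.

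**The case against.** **The wrong name is an obvious slip.** The heading, unit and route show what was meant, the card used at the bedside names salbutamol correctly, and staff are trained in this preparation. All of this stands and makes actual harm unlikely. It does not make the step right, and a preparation procedure should not depend on the reader correcting it.

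**Only one dose is intended.** Section 7 lets the single fixed dose be given early; it does not add another. The physician's box and the nurse's card may describe the same dose, once as plan and once as administration. This also stands. A reader might infer that the plan orders salbutamol twice. The documents do not support that: sections 5 and 7 specify one dose, and 20 mg appears nowhere. What remains is that no instruction prevents a repeat.

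**Records exist.** Section 6 has the nurse document the starting time when giving the medications, section 22 includes checks of dosing documentation and drug accountability, and the data sheet has a general medications line. These could reveal a repeat afterwards. They would not prevent one.

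**Baseline potassium.** A reader might infer that early salbutamol leaves the baseline potassium undefined. The SAP describes baseline, under its secondary outcomes, as the value before any medication and uses the same term for the covariate in the primary model. Section 7 of the Protocol collects basic laboratory tests before the study protocol starts. That reading is not supported.

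**Conclusion.** The concern holds in two limited parts. Step 2 of the salbutamol method is wrong as written: one drug name, certain from the text. The instructions also fail to prevent a second salbutamol dose, so a patient taken literally through the flow chart and then the card could receive 20 mg instead of 10 mg. The second part assumes that the early dose was given and that the nurse follows the card as printed. The documents give no indication of how often this would happen.

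A reader might infer bias between arms or a loss of power from extra salbutamol. Neither is claimed. The regimen is common to both arms, and the documents give no figure from which an effect on the primary comparison could be calculated. This is a matter of patient safety and of consistent instructions. It should be corrected because the text is operational and the correction costs almost nothing.

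**What to change.** 1. In section 8, change step 2 of the salbutamol nebulization method to: *Take 10 mg of salbutamol.*
2. On the 5-unit medication card (both printed copies) and on the 10-unit card, which is not shown, change the salbutamol line to: *Salbutamol 10 mg nebulization over 15 minutes, only if not already given.*
3. Add a field for the time salbutamol was given to the data collection sheet.

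The cost is one word in section 8, one phrase on each card and one field on the data sheet. Sample size, blood sampling and analysis do not change.

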## 9. Storage, Handling, and Administration

### The principle investigator and co-investigators will ensure that:

- The study treatment is handled and stored safely and properly.
- The study treatment is only dispensed to study subjects in accordance with the protocol.
- The study treatment will be stored in accordance to product labelling.
  - o Exposure to light, freezing and extreme heat should be avoided.
  - o Will Be stored the at pharmacy in controlled room temperature.
- There will be only one use per ampule of treatment per subject.
- The study treatment will be checked for expiration dates prior to use.

## Packaging and Labelling

A calculated sample size equivalent both insulin doses 5 units VS 10 units will be prepared and set ready to be used based on randomization blocks. Each package has its own unique number corresponding to (case and control) sampling.

### Each package contains:

- **Envelope with:**
  - o Data collection sheet with unique generated number.
  - o Consent form.
  - o Instructions sheet
  - o Medication administration form (for the nurses).

Blood investigation will be sent to biochemistry lab for potassium level and other investigations, and it's the only acceptable way in the study. The study investigators will verify that study treatments are received intact and in the correct amounts.

## **10. Variable definitions and measurements**

Intravenous Regular Insulin will be used for our intervention. Potassium level will be measured by the main laboratory. Our outcome will be measured based on amount of potassium level reduction.

Hypoglycemia will be defined as (random blood sugar (RBS)  $\leq 3.89$  mmol/l in Diabetic patients and less than 3 mmol/l in non-Diabetic patients).

## **Data collection tools and methods**

All data will be collected from the hospital information system. Data will be kept in secured files with encryption keys/password to maintain all patients' privacy. Only who is involved in the study will be able to access the files.

## **Data quality**

In each site there will be a focal point. A physician will be responsible for that site. Before the study starts our investigators will do training sessions about the study and will clarify all the details that the site physicians inquire. Research assistances will be hired for data collections to facilitate the process of data collection and to monitor the flow of the study protocol in each site.

## **Data analysis**

Statistical Package for the Social Sciences (SPSS) applications version 29 will be used for our analysis.

## **11. Ethical considerations**

Ethical approval will be needed from both hospitals before starting our research. Any adjustment advised by all ethical committees the research team will apply it to ensure patient safety. At any time during our study if the investigator noticed any increase risk on the patient safety the investigator will stop our study protocol.

Because the study will not deviate from what is practiced by some physician and what is recommended by some guidelines our researchers team do not anticipate major harm on the patients. Even with this our investigator will follow our patients/participants and will stop the study if any indicator for harm rose at any time of the study. Our study will help if it proved no difference in the effect of both doses in 2 main things. The 1st one less hypoglycemia for the patients in the future and the 2nd main point cost effect as less doses of the same medication will be required to achieve the same goal.

By the end of the study all participants will be contacted and our investigators will share the results with them and how their contribution helped the advancement of medical field.

## **12. Conflict of interest:**

No conflict of interest

### **13.Incentives:**

No incentives of any kind will be given to the participants.

### **14.Results Dissemination**

After completing the study the research team will publish the results in international journals and will have poster presentations.

### **15.Management and monitoring of the research activities:**

The full team will manage the study flow. Each researcher will be responsible for a hospital work flow at a certain time then the researchers will swab after a period of time. Daily monitor will be done for all the cases via direct visit or follow up via the phone or Virtual meeting. Once enough sample collected the investigators will start our initial analysis of them.

### **16.Limitations and difficulties of the study:**

The large sample size will need to be followed and all data must be kept and organised all time.

Multicentre will have some difficulties as 2 different HIS used in these hospitals.

Funding will be needed for to cover all the logistics and facilitate the flow of the research..

### **17. Safety Assessments**

#### **Adverse Events**

All adverse events will be documented on serious adverse event case log. All serious adverse events should be immediately reported to the primary investigator. Any serious, adverse event will be reported immediately to the Institutional Review Board.

**An Adverse Events is considered serious if it causes a threat to the patient's life or functioning. The U.S. Food and Drug Administration (FDA) define a serious adverse event (SAE) as any untoward medical occurrence that:**

- Results in death.
- Life threatening (places the patient at risk of death).
- Requires hospitalization or prolongs an existing hospitalization.
- Causes persistent or significant disability or incapacity.
- Requires medical intervention to prevent one of the above outcomes.

## **18. Rationale for subject selection and recruitment.**

This is a prospective efficacy, safety and tolerability trial in adults. Active treatment (a single dose of intravenous insulin 5 units or 10 units) will be used. The population selected for this study, adult patients is a patient population that may benefit from the use of insulin. This is a population in whom intravenous 5 units of insulin has been approved for and in whom insulin has been shown to be safe and effective when used for hyperkalemia management, specifically renal failure patient. This is also a population in whom other dose insulin, 10 units of insulin have been shown to be efficacious and safe. Therefore, it seems highly likely that the intravenous 5 units of insulin, is an appropriate dose and it will also be effective, safe and well tolerated.

## **19. Efficacy and safety assessment.**

### **Efficacy Variables**

#### **Primary Efficacy Variable**

The primary efficacy variable is the assessment of reduction of the potassium level after intravenous regular insulin dose (either 5 units or 10 units) at 2 hours from medication administration. Blood sample will be collected from the patient and will be sent to the main laboratory for analysis.

#### **Secondary Efficacy Variables**

The secondary efficacy measurement of risk of hypoglycemia event and the risk factors of hypoglycemia.

#### **Safety Variables**

The safety variables are the occurrence of adverse events.

## **20. Statistical analysis:**

### **Subgroup analyses planned.**

No subgroup analyses planned.

### **Number of subjects to be enrolled.**

336 subjects will be needed (168 in each arm).

## Rationale for the choice of sample size

The Sample size was calculated based on a study published in Critical Care Explorations Journal 2020 with the article named Comparison of IV Insulin Dosing Strategies for Hyperkalemia in the Emergency Department by Kayvan Moussavi et al (8). The anticipated effect size  $d = 0.2$  with alpha error prob = 0.0250 (one-side), actual power 90, Standard deviation of 0.62 and allocation ratio 1:1. The calculated sample size is 320 (160 in each arm). Our statistician estimated a 5% drop rate. So the sample size increased to 336 (168 in each arm).

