Ziv Harel and Kamel S. Kamel 2016 in their systemic review of articles that looked into the different doses of insulin found no difference in the efficacy of lowering potassium between 10, 12, and 20 units of insulin (11)

Kayvan Moussavi et al 2020 in their observation study showed that less than 10 units of insulin cause less incidence of hypoglycemia but the amount of potassium reduction was less in patients who received less than 10 units (8). But this study was a retrospective for patients who attended the emergency department in a single center. Although they mentioned less than 10 units have less efficacy but the doses of less than 10 units range from 3 units to 8 units as it will be difficult to conclude this range of values. (8).

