## Study hypothesis

No difference between 5 and 10 units of intravenous regular insulin in lowering potassium levels in patients with hyperkalemia at 2 hours.

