### **Sampling and sample size**

Our target will be all patients with hyperkalemia presenting to the emergency departments in both hospitals. The Sample size was calculated based on a study published in Critical Care Explorations Journal 2020 with the article named *Comparison of IV Insulin Dosing Strategies for Hyperkalemia in the Emergency Department* by **Kayvan Moussavi** et al (8). The anticipated effect size  $d = 0.2$  with alpha error prob = 0.0250 (one-side), actual power 90, Standard deviation of 0.62 and allocation ratio 1:1. The calculated sample size is 320 (160 in each arm). Our statistician estimated a 5% drop rate. So the sample size increased to 336 (168 in each arm).

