5 versus 10 units of insulin in hyperkalemia management: multi-center, prospective, double blinded, non-inferiority, randomized control trial in adult patients with age of 18 years and more at two emergency departments Sultan Qaboos university hospital and Royal hospital. We will include patients with potassium level 5.5 mEq/l and more. We will measure the mean reduction of insulin level among both groups at 2 hours from treatment. Written consent will be obtained from all patients. Eligible subjects will be enrolled. Control group will receive 10 units intravenous insulin with Dextrose 50 % 50 ml over 15 minutes and Salbutamol nebulization. Intervention group will receive 5 units intravenous insulin with Dextrose 50 % 50 ml over 15 minutes and Salbutamol nebulization. Patient will be monitored and basic labs will be recorded. Blood sugar will be monitored at 0, 60 and 120 (2 hours) minutes. Potassium level will be measured at presentation and at 120 minutes (2 hours) from insulin administration.

Sample size calculation

We aim to study all hyperkalemia patients who come to the emergency departments of both hospitals. The sample size determination was influenced by a 2020 article in the Critical Care Explorations Journal titled "Comparison of IV Insulin Dosing Strategies for Hyperkalemia in the Emergency Department" authored by Kayvan Moussavi and colleagues. We expect an effect size of $d=0.2$, with an alpha error probability of 0.0250 (one-sided), a true power of 90, a standard deviation of 0.62, and a 1:1 allocation ratio. The sample size deduced is 320, split evenly between both groups. Anticipating a 5% attrition rate, we've adjusted our total sample to 336 participants, with 168 in each group

Aims and objectives

The aim of this study is to compare the efficacy of two insulin doses (5 units and 10 units) in reducing serum potassium level in patients receiving hyperkalemia treatment.

Outcomes

Primary outcome

- To study the efficacy of two intravenous insulin doses (5 units and 10 units) in reducing serum potassium level in patients receiving hyperkalemia treatment using the main laboratory measurements. (the aim of reduction of 0.6 mmol/l +/- 0.2 mmol/L) (1). Blood sample will be collected and send to the main laboratory for analysis at two hours from medications administration. The efficacy of the 2 doses will be measured at 2 hours from administration of medications by comparing the amount of changes in potassium level at two hours.

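### The stated 90% power does not follow from the plan's own inputs: 160 per arm gives about 82% at zero true difference, and no allowance is made for a shortfall of the 5-unit dose

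*Protocol*

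**What the plan says.** The sample size is given in three places: Protocol section 5 (Sampling and sample size), Protocol section 20 (Rationale for the choice of sample size) and SAP, Sample size calculation.

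- **Source.** The Protocol says "The Sample size was calculated based on a study published in Critical Care Explorations Journal 2020". The SAP is looser: "The sample size determination was influenced by a 2020 article in the Critical Care Explorations Journal". Neither says which input came from that study.
- **Inputs.** The Protocol calls 0.2 "The anticipated effect size" and adds "alpha error prob = 0.0250 (one-side), actual power 90", with SD 0.62 and 1:1 allocation. The SAP has "We expect an effect size of $d=0.2$, with an alpha error probability of 0.0250 (one-sided". Neither says whether 0.2 is a margin or an expected difference, or whether it is in mmol/L or SD units.
- **Result.** 320 patients (160 per arm), raised to 336 for 5% dropout.
- **True difference.** None is stated in the calculation. The Protocol's study hypothesis is "No difference between 5 and 10 units of intravenous regular insulin in lowering potassium levels", and section 25 anticipates non-inferiority.
- **The sizing study.** Protocol section 2 describes it as retrospective and single-centre, and reports that "the amount of potassium reduction was less in patients who received less than 10 units". It then discounts this: "the doses of less than 10 units range from 3 units to 8 units as it will be difficult to conclude this range of values". The same section cites other, mostly retrospective, studies that found 5 and 10 units equally effective.
- **Margin and model.** The only margin is in the SAP's primary analysis, -20 units, which cannot be used for potassium in mmol/L. The SAP adjusts the primary analysis for baseline potassium, but the sample size calculation does not mention this.

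**The concern.** Anyone judging whether the trial can answer its question will rely on the 90%. Two things make that figure doubtful.

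First, it should follow from the inputs printed beside it, and on a direct check it does not.

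Second, non-inferiority power depends heavily on the true difference assumed. The calculation names none and shows no sensitivity, while the study named as its basis is reported to have found a smaller effect at lower doses. If 5 units is slightly weaker than 10 but still within the margin, the chance of showing non-inferiority is well below the advertised figure, and an inconclusive result becomes more likely than the sponsor and ethics committees have been told.

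**Working it through.** **Inputs from the documents:** 0.2; SD 0.62; one-sided alpha 0.025 (z = 1.960); power 90% (z = 1.282); 160 per arm.

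**Assumptions:** 0.2 is the non-inferiority margin and, like the SD, is in mmol/L; normal approximation; no covariate adjustment.

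**1. The plan's own figure.** For zero true difference:

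n per arm = 2 × [SD × (1.960 + 1.282) / margin]² = 2 × [0.62 × 3.242 / 0.2]² ≈ 202, or 404 in total.

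The stated 320 is not reproduced.

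- A noncentral t calculation gives 203 per arm.
- Reading 0.2 as standardised gives 2 × [3.242 / 0.2]² ≈ 526 per arm.
- The nearest variant tried is one-sided alpha 0.05, which needs 165 per arm and gives 89.3% power at 160. That contradicts the stated alpha.
- The dropout step is 320 × 1.05 = 336; dividing by 0.95 gives 337. This is immaterial.

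**2. Power at 160 per arm.** SE = 0.62 × √(2/160) = 0.0693. For a true shortfall t of the 5-unit arm,

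power = Φ((0.2 − t)/0.0693 − 1.960).

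| Assumed shortfall t (mmol/L) | (0.2 − t)/SE − 1.960 | Power |
|---|---|---|
| 0 | 0.925 | 82.3% |
| 0.02 | 0.637 | 73.8% |
| 0.05 | 0.204 | 58.1% |
| 0.10 | −0.517 | 30.3% |

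The shortfalls are an assumed range, because the documents do not give the size of the difference seen in the sizing study. Even with no dropout at all (168 per arm), power at zero is 84.1%.

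**3. What 90% at 160 per arm would require.** Either a true difference of 0.2 − 3.242 × 0.0693 = −0.025, that is, 5 units better by about 0.025 mmol/L, or an SD of about 0.55. Neither is stated.

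**4. Standardised reading.** If 0.2 is in SD units (0.2 × 0.62 = 0.124 mmol/L), power at zero is Φ(0.2/√(2/160) − 1.960) = Φ(−0.171) = 43.2%.

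**5. Baseline adjustment.** A correlation r between baseline potassium and the outcome multiplies the SD by √(1 − r²). At an assumed r = 0.5, SE = 0.0693 × 0.866 = 0.0600, and power is 91.5%, 70.5% and 38.4% at shortfalls of 0, 0.05 and 0.10. The r that would make 160 per arm enough at zero difference is √(1 − 160/201.95) ≈ 0.46. The documents give no correlation.

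**The case against.** **Baseline adjustment may restore 90%.** This is the best reply. The SAP does adjust for baseline potassium, and a correlation of about 0.46 would be enough at zero difference. It stands as a possibility, but the plan neither claims the gain nor states a correlation. It also does not remove the dependence on the true difference: at an assumed 0.5, power is still 70.5% at a shortfall of 0.05.

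**The scale of 0.2 is not stated.** That is so, and every power figure here is conditional on it. The standardised reading makes the position worse, however, and neither reading gives 90%.

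**Zero difference has cited support.** This stands. A reader might infer that the sizing study contradicts the no-difference hypothesis, so that its own source refutes the 90%. The documents do not go that far. They do not say that the study supplied anything beyond, perhaps, the SD. Its low-dose group pooled 3 to 8 units, so it is not a test of 5 units. The Protocol openly discounts its result and cites other studies that found no difference. What remains is doubt about zero, not a contradiction.

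**The sizing study may be the better match on setting.** A reader might also infer that the sizing should move to the studies comparing 5 with 10 units directly. The documents do not show that this would be an improvement. Most of those studies were in renal insufficiency, whereas the sizing study was done in an emergency department, as this trial is, and the documents give no SD or difference from the others.

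**Conclusion.** The concern holds for the stated power. On the plan's own inputs, with 0.2 read as a margin in mmol/L and no adjustment, 160 per arm gives about 82% at zero true difference rather than 90%, and 90% needs 202 per arm. Power falls to about 58% at an assumed shortfall of 0.05 and 30% at 0.10 mmol/L, and the plan makes no allowance for either.

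Two stronger conclusions are not supported. One is that the plan expects a shortfall of 0.2 mmol/L, which would put power at 2.5%. That takes the label on the effect size literally, against a hypothesis of no difference. The other is that the trial will often fail. That depends on a true shortfall whose size the documents do not give, and a very small one is equally consistent with what they report.

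**What to change.** In Protocol sections 5 and 20 and in SAP, Sample size calculation:

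1. Keep the sample size at 320 evaluable and 336 enrolled.
2. Say that 0.2 mmol/L is the non-inferiority margin, and that the assumed true difference is zero. If 0.2 was meant as a standardised effect, say so and recompute, because the figures below would not apply.
3. Replace the single 90% with the power on 320 evaluable patients: about 82% at zero difference, 58% at a shortfall of 0.05 mmol/L and 30% at 0.10 mmol/L.
4. If the gain from baseline adjustment is to be credited, state the assumed correlation and its basis. At an assumed 0.5 the three figures are about 91%, 70% and 38%.

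The source study need not change. The cost is wording in two Protocol sections and one SAP section, with no extra patients or procedures. The downside is a less favourable stated power.
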